15.1.4. SENSITIVITY ANALYSIS OF PRIMARY EFFICACY VARIABLE(S)

15.1.4.1. Graphical examination

Patterns of missing data in the primary endpoint will be assessed through graphical tools based on the reason and timing of study withdrawal by subjects.

Change from baseline in SAPS-PD total score by visit will be described and plotted by reasons of early discontinuation (adverse event, lack of efficacy, progressive disease, withdrawal by subject, protocol deviation, noncompliance with study medication, death, pregnancy, other reasons) and for completers, separately for each treatment group. Similar reasons may be combined, depending on the number of subjects under each reason.

Change from baseline in SAPS-PD total score by visit will also be described and plotted by time of termination (Week 1 terminators, Week 2 terminators, Week 3 terminators, Week 5 terminators, Week 6 terminators) and for completers, separately for each treatment group.

- o Week 1 terminators: subjects who discontinued before or on Visit 3;
- o Week 2 terminators: subjects who discontinued after Visit 3 but before or on Visit 4;
- o Week 3 terminators: subjects who discontinued after Visit 4 but before or on Visit 5;
- o Week 5 terminators: subjects who discontinued after Visit 5 but before or on Visit 6;
- o Week 6 terminators: subjects who discontinued after Visit 6 but before or on Visit 7;
- o Completers: subjects who discontinued after Visit 7.

Document:

\

Author:

Version Number:

Final 1.0

Version Date:

24FEB2020

Template No: CS_TP_BS016 Revision 4
Effective Date: 01Apr2016

Reference: CS_WI_BS005

15.1.4.2. Pattern-mixture model with placebo-based multiple imputation

The MMRM model used in the primary analysis makes the assumption that data are missing at random (MAR). However, the missing data mechanism may or may not be at random. Sensitivity to the missing data assumptions will be tested by using the pattern-mixture model with placebo-based multiple imputation method (Ratitch, O'Kelly, & Tosiello, 2013), exploring the robustness of the MMRM results of the primary efficacy analysis. In this analysis, missing values in the SEP-363856 (25, 50 or 75 mg/day) treatment group will be imputed based on data of the placebo group, assuming that, after withdrawal, subjects from the SEP-363856 (25, 50 or 75 mg/day) group will exhibit the same future evolution of Parkinson's as subjects from the placebo group, and that subjects who discontinue from the placebo group will exhibit the same future evolution of Parkinson's as subjects in the placebo group remaining in the study. This approach does not assume a sustained benefit of experimental treatment after discontinuation.

Two separate imputation procedures are used to impute missing values. Firstly, the Markov chain Monte Carlo (MCMC) method is used to perform partial imputation to obtain datasets with monotone missing patterns. Then a sequential regression multiple imputation method is used to impute the monotone missing values.

Under the assumption that the SAPS-PD total scores have a multivariate normal distribution, the MCMC method is used to impute only intermittent missing values (using the SAS MI procedure with MCMC statement), by using a data augmentation algorithm, with each iteration n consisting of an imputation step and a posterior step. The imputation step uses a random draw of $\theta^{(n)}$, parameter of the joint imputation model, to sample missing values from a conditional distribution $P(Y_{mis}|x, y_{obs}, \theta^{(n)})$, obtaining $y_{mis}^{(n)}$, the subset of missing values that need to be filled in to achieve monotone missingness. The posterior step simulates a new draw of the parameter $\theta^{(n+1)}$ from the posterior distribution given the current monotone missing data $P(\theta|x, y_{obs}, y_{mis}^{(n)})$ with a non-informative Jeffreys prior. Treatment group will be taken into account for the imputation. These steps are repeated to obtain 1000 datasets with monotone missingness. The options for burn-in and thinning will be optimized by examining the diagnostic plots. The random seed number is 12345.

The remaining monotone missing data will be imputed using sequential regression multiple imputation, where a separate regression model is estimated for imputation of each variable (i.e., SAPS-PD total score at each time point). Imputation of values in the placebo group will assume MAR. Imputation of values in the SEP-363856 (25, 50 or 75 mg/day) group will be done as if the subject had been a member of the placebo group. Missing values in the SEP-363856 (25, 50 or 75 mg/day) group will be imputed using the imputation model of the placebo group, i.e., conditional on subject values observed at time points prior to discontinuation relative to the mean of the model for the placebo group. Each sequential regression model (i.e., for imputation of values at a given time point) will include explanatory variables for all previous (Baseline, Week 1, 2, 3 and 5) values of SAPS-PD total score. Missing values at a given time point in placebo and SEP-363856 (25, 50 or 75 mg/day) arms will be imputed from the same imputation model, conditional on subject values observed or imputed at previous time points. The SAS MI procedure with the MONOTONE REG statement is used to specify that the regression method will be used for the imputation, and the MNAR statement with MODEL option will be used for the SAPS-PD total score at each post-baseline visit to specify that only observations from the placebo group should be used to estimate the imputation model. The random seed number is 12345.

No rounding restriction will be applied to imputed SAPS-PD total scores. The imputed SAPS-PD total scores must be within the range of 0 to 45.

Document:

\

Author:

Version Number:

Final 1.0

Version Date:

24FEB2020

Template No: CS_TP_BS016 Revision 4
Effective Date: 01Apr2016

Reference: CS_WI_BS005

Each of the 1000 imputed datasets will be analyzed using the same MMRM model as the primary efficacy analysis. Results from the analysis of each imputed dataset, i.e. the LS means of each treatment group, the LS mean treatment difference, and their standard errors, will be combined using Rubin's imputation rules (using the SAS MIANALYZE procedure) to produce pooled LS mean estimates, their standard errors and 95% CI, and a pooled p-value for the test of null hypothesis of no treatment effect.

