3.4. DETERMINATION OF SAMPLE SIZE

A total of approximately 36 subjects will be randomized in 2:1 ratio to SEP-363856 and placebo, with approximately 24 subjects assigned to SEP-363856 and 12 subjects assigned to placebo. The sample size will provide powers of 59%, 48%, 37%, and 27% to detect treatment effect sizes of 0.8, 0.7, 0.6, and 0.5, respectively, in change from Baseline in SAPS-PD at Week 6 for SEP-363856 versus placebo. It was estimated by using a two independent sample t-test method with 2-sided significant level of 0.05. The sample size was determined for the purposes of exploring the efficacy, safety and tolerability of flexible dosing with SEP-363856 (25, 50, or 75 mg/day) for 6 weeks in male and female subjects with a clinical diagnosis of PDP. A sufficient number of subjects will be enrolled to ensure 36 randomized subjects.

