15.1.3. PRIMARY ANALYSIS OF PRIMARY EFFICACY VARIABLE(S)

The primary objective of this study is to test whether the mean changes from baseline in SAPS-PD total score at Week 6 in the SEP-363856 (25, 50 or 75 mg/day) group and the placebo group are equal.

Let μ_{SEP} and μ_{PBO} represent the mean changes from baseline at Week 6 in SAPS-PD total score for the SEP-363856 (25, 50 or 75 mg/day) and placebo groups, respectively. The following hypothesis will be tested:

Document:

\

Author:

Version Number:
Version Date:Final 1.0
24FEB2020Template No: CS_TP_BS016 Revision 4
Effective Date: 01Apr2016

Reference: CS_WI_BS005

H₀: $\mu_{\text{SEP}} = \mu_{\text{PBO}}$ versus **H₁:** $\mu_{\text{SEP}} \neq \mu_{\text{PBO}}$

The primary efficacy analysis will be performed on the mITT population.

Change from baseline in SAPS-PD total score at Week 6 will be analyzed using an MMRM model, with fixed factors for visit (Weeks 2, 3, 5 and 6; as a categorical variable), treatment, and treatment-by-visit interaction, and with baseline SAPS-PD total score as a covariate. An unstructured covariance matrix will be used to model the within-subject correlation. The Kenward-Roger approximation will be used to calculate the denominator degrees of freedom.

In case the model above fails to converge, a spatial exponential covariance structure and a spatial power covariance structure will be assumed sequentially. The first covariance structure to yield convergence will be used in the analysis.

Within group effect size at each time point will be calculated as the least squares (LS) mean of each treatment group divided by the model estimate of standard deviation, obtained as the square root of the corresponding diagonal element of the residual covariance matrix (R matrix from PROC MIXED).

Between group effect size at each time point will be calculated as the LS mean difference divided by the model estimate of standard deviation, obtained as described above.

LS means (\pm SE) of change from baseline in SAPS-PD total score will be plotted by week and treatment group.

The above analysis will also be performed on the SAPS-PD subscale score for hallucinations and the SAPS-PD subscale score for delusions.

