15.1.4.3. Tipping point analysis

Sensitivity to departures from the MAR assumption will also be investigated using a tipping point analysis. In this analysis, departures from MAR in the SEP-363856 (25, 50 or 75 mg/day) group will be assessed assuming that subjects who discontinue the study have, on average, efficacy outcomes after discontinuation that are worse by some amount δ compared to other similar subjects with observed data at the same time point (i.e., compared to a value which would have been assumed under a MAR model).

A series of analyses will be performed with increasing values of δ until the analysis conclusion of a statistically significant treatment effect no longer holds. The value of δ that overturns the primary results will represent a tipping point. An interpretation of clinical plausibility of the assumption underlying the tipping point will be provided.

Change from baseline in SAPS-PD total score will be analyzed based on data observed while the subject remains on study as well as data imputed using multiple imputation methodology for the time points at which no value is observed. Intermittent (non-monotone) missing data will be imputed first based on the MAR assumption and a multivariate joint Gaussian imputation model using the MCMC method within each treatment arm, as described above for the pattern-mixture model with placebo-based multiple imputation.

The remaining monotone missing data will be imputed using sequential regression multiple imputation, where a separate regression model is estimated for imputation of each variable (i.e., SAPS-PD total score at each time point). Each regression model will include explanatory variables for treatment and all previous (Baseline, Week 2, 3, and 5) values of SAPS-PD total score. After the MAR-based imputations have been generated for SAPS-PD total score at each time point, a value of δ will be added to all imputed values in the SEP-363856 (25, 50 or 75 mg/day) group. This approach assumes that the marginal mean of unobserved subject measurements is worse by δ at each time point after discontinuation compared to the marginal mean of subjects with observed data at the same time point.

No rounding restriction will be applied to imputed continuous values. The imputed SAPS-PD total scores must be within the range of 0 to 45.

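### The placebo-based imputation regressions are fitted on about 12 placebo subjects alone (7 residual df at Week 6, about 5 if two values are missing), so this sensitivity analysis adds estimation noise to the assumption it tests

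*SAP*

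**What the plan says.** SAP 15.1.4.2 imputes monotone missing SAPS-PD totals visit by visit. Each regression "will include explanatory variables for all previous (Baseline, Week 1, 2, 3 and 5) values of SAPS-PD total score", and the text specifies that "only observations from the placebo group should be used to estimate the imputation model". The same fitted model serves missing values in both arms. The completed datasets (1000) are analysed with the primary MMRM and pooled by Rubin's rules into an estimate, standard error, confidence interval and p-value.

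SAP 3.4 plans "approximately 24 subjects assigned to SEP-363856 and 12 subjects assigned to placebo". No expected dropout rate, minimum number of placebo completers or reduced imputation model is given.

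The tipping-point analysis in SAP 15.1.4.3 uses a different regression: "Each regression model will include explanatory variables for treatment and all previous (Baseline, Week 2, 3, and 5) values of SAPS-PD total score". That model is not restricted to one arm.

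The Appendix 3 code disagrees with the text. Its definition table codes `TRT01PN` 1 as SEP-363856 and 2 as placebo, yet step 2 of the placebo-based imputation restricts the model to `TRT01PN='1'`.

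**The concern.** A regression with five coefficients estimated on about ten people gives unstable slopes and a poorly known residual variance. Proper multiple imputation carries that uncertainty into every imputed value, including those of all SEP-363856 dropouts. The analysis is meant to show what happens to the treatment effect if active dropouts follow the placebo course. If its p-value exceeds 0.05 after a significant MMRM, the reader cannot tell whether the assumption reduced the effect or the small fitting sample widened the interval. Since 15.1.4.3 uses a different imputation model, a difference between the two sensitivity analyses would mix the same two causes.

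**Working it through.** **The plan's own figure.** Two-sample t-test, n = 24 and 12, two-sided 0.05, 34 df, noncentrality d × √(24×12/36) = 2.83d. For d = 0.8, 0.7, 0.6 and 0.5 this gives 59.4, 48.6, 37.8 and 28.0%, against the stated 59, 48, 37 and 27%. The sample sizes are therefore used as the plan intends.

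**Residual degrees of freedom at Week 6.** Week 1 in the predictor list is Visit 3, the baseline visit (Protocol Table 2; SAP 5.5), so it adds no separate predictor. Coefficients: intercept, Baseline, Weeks 2, 3 and 5 = 5. Residual df = 12 − missing − 5. The drawn variance is the residual sum of squares divided by a chi-square on df, so on average it is df/(df − 2) times the estimate.

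| Placebo values missing at Week 6 | df | Inflation |
|---|---|---|
| 0 | 7 | 7/5 = 1.40 |
| 1 | 6 | 6/4 = 1.50 |
| 2 | 5 | 5/3 = 1.67 |
| 3 | 4 | 4/2 = 2.00 |
| 4 | 3 | 3/1 = 3.00 |

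With a both-arm fit and 4 active and 2 placebo values missing, df = 30 − 6 = 24 and the factor is 24/22 = 1.09.

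**Simulation.** Dropout, variance and correlation are not in the documents. Assumed: effect size 0.8, baseline to Week 6 correlation about 0.49, completely random monotone dropout, Week 6 ANCOVA on the completed data, 600 trials with 300 imputations each. Lost is the share of MMRM-significant trials that are not significant under the placebo-based analysis. Noise share = (lost placebo-only − lost both-arm) / lost placebo-only.

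| Dropouts (SEP, placebo) | SE placebo-only | SE both-arm | Ratio | Lost placebo-only | Lost both-arm | Noise share |
|---|---|---|---|---|---|---|
| 2, 0 | 0.338 | 0.320 | 1.06 | 7.2% | 3.6% | 50% |
| 2, 1 | 0.363 | 0.329 | 1.10 | 16.7% | 5.5% | 67% |
| 4, 2 | 0.422 | 0.350 | 1.21 | 46.5% | 13.6% | 71% |
| 4, 2, values clipped at assumed limits | 0.391 | 0.345 | 1.13 | 34.5% | 13.1% | 62% |
| 6, 3 | 0.503 | 0.376 | 1.34 | 74.5% | 33.3% | 55% |
| 8, 2 | 0.469 | 0.377 | 1.24 | 77.3% | 49.2% | 36% |

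The Monte Carlo error on the loss percentages is about 2 to 3 points. At (4, 2):

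- The MMRM estimate is −0.81. Both placebo-based fits give −0.71, as does the same assumption with the true parameters known (SE 0.335, 10.2% lost).
- Reported SE against the actual spread of estimates: 0.422 against 0.308 placebo-only, and 0.350 against 0.292 both-arm.
- Correlations of 0.29 and 0.73 give noise shares of 66% and 70%. An effect of 1.2 gives 21.0% against 5.2% lost (75%).

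**Runs on the SAPS-PD point scale.**

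- Assumed difference −5, SD 7, values kept within 0 to 45. At 15% missing, 27–34% of MAR-significant trials are lost placebo-only against 9–19% both-arm, with SE 10–11% larger. At 25% missing, 49–59% against 23–34%, with SE 18–22% larger. Pairing the range ends, 23/49 = 47% to 34/59 = 58% of the loss remains after the fix, so noise is about 42–53%.
- A separate run with 4 and 2 dropouts gives estimates of −3.94 and −3.93, and SE 2.66 against 2.38 (ratio 1.12) with an actual SD of about 2.1. The losses are 49% and 25%, so noise is (49 − 25)/49 = 49%.

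**The case against.** **Five df is not a given.** Twelve subjects leave 7. SAP 6.4 maps early-termination assessments to the next planned visit, so someone leaving after Visit 6 can still supply a Week 6 value. In the other direction, SAP 6.9 sets off-period ratings to missing. The condition must therefore be stated.

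**The placebo course includes slopes.** SAP 15.1.4.2 assumes that active dropouts evolve as placebo subjects do, given their earlier scores. A both-arm fit lets the 24 active subjects dominate those slopes. It is a modelling choice, and it adds common slopes and residual variance to this test. That stands. However, the primary MMRM already uses one covariance matrix and 15.1.4.3 already uses such a regression. In runs with unequal correlations between arms, the both-arm fit moved the mean estimate by less than 0.2 points and rejected a true null 4% of the time.

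**Counting lost significance exaggerates.** At effects near the plan's 48 to 59% power, many significant trials lie close to 0.05. The SE ratio is the plainer measure.

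**The consequence is limited.** The distortion is conservative, the interval is reported, and 15.1.4 contains several other sensitivity analyses. No section says that a non-significant result here means the finding is not robust. This limits the weight of the point but does not remove the ambiguity in this analysis.

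**Conclusion.** The point holds as a weakness in one sensitivity analysis; the primary test is unaffected. With 12 placebo subjects the Week 6 regression has 7 residual df, or about 5 if two placebo values are missing. With balanced dropout of about 17 to 25%, the SE is about 10 to 22% larger than with a both-arm fit (34% in one scenario). The estimate is essentially the same, and roughly half or more of the lost significance is noise. These sizes rest on assumed variance, correlation and missingness.

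A reader might infer that a failure here would be due to noise and not to the assumption. That goes too far. The assumption alone moves the estimate from −0.81 to −0.71 at (4, 2) and explains about half of the loss in several runs. With dropout concentrated on active treatment (8, 2), 64% of the loss remains after the both-arm fit. With (2, 0) only about 7% of significant trials are lost at all. All of this concerns the SAP text; the Appendix 3 code, run as printed, would fit the regressions on the active arm.

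**What to change.** In SAP 15.1.4.2, fit each sequential regression on all subjects observed at that visit, with all previous SAPS-PD scores and a treatment term, as 15.1.4.3 already does. Impute missing SEP-363856 values with the treatment term set to placebo. Drop Week 1 from the predictor list, since it duplicates Baseline. Report the shift in estimate and the change in SE relative to the MMRM separately, so that the assumption and the noise can be told apart.

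Change Appendix 3 step 2 to match, and settle the arm coding throughout the appendix: the primary MMRM contrasts treat level 2 as SEP-363856, while the definition table and step 3 treat level 1 as SEP-363856.

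The cost is a few lines of SAP text and one revised imputation call per visit. The price in assumptions is common slopes and residual variance across arms. If that is a worry, keep the placebo-only fit as a secondary display.

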15.1.4.3. Tipping point analysis

Sensitivity to departures from the MAR assumption will also be investigated using a tipping point analysis. In this analysis, departures from MAR in the SEP-363856 (25, 50 or 75 mg/day) group will be assessed assuming that subjects who discontinue the study have, on average, efficacy outcomes after discontinuation that are worse by some amount δ compared to other similar subjects with observed data at the same time point (i.e., compared to a value which would have been assumed under a MAR model).

A series of analyses will be performed with increasing values of δ until the analysis conclusion of a statistically significant treatment effect no longer holds. The value of δ that overturns the primary results will represent a tipping point. An interpretation of clinical plausibility of the assumption underlying the tipping point will be provided.

Change from baseline in SAPS-PD total score will be analyzed based on data observed while the subject remains on study as well as data imputed using multiple imputation methodology for the time points at which no value is observed. Intermittent (non-monotone) missing data will be imputed first based on the MAR assumption and a multivariate joint Gaussian imputation model using the MCMC method within each treatment arm, as described above for the pattern-mixture model with placebo-based multiple imputation.

The remaining monotone missing data will be imputed using sequential regression multiple imputation, where a separate regression model is estimated for imputation of each variable (i.e., SAPS-PD total score at each time point). Each regression model will include explanatory variables for treatment and all previous (Baseline, Week 2, 3, and 5) values of SAPS-PD total score. After the MAR-based imputations have been generated for SAPS-PD total score at each time point, a value of δ will be added to all imputed values in the SEP-363856 (25, 50 or 75 mg/day) group. This approach assumes that the marginal mean of unobserved subject measurements is worse by δ at each time point after discontinuation compared to the marginal mean of subjects with observed data at the same time point.

No rounding restriction will be applied to imputed continuous values. The imputed SAPS-PD total scores must be within the range of 0 to 45.

One-thousand (1000) imputed datasets will be generated. The random seed number for both the partial imputation step and the sequential regression multiple imputation step will be 12345.

Each of the 1000 imputed and δ -adjusted datasets will be analyzed using the same MMRM model as the primary efficacy analysis. Results from the analysis of each imputed dataset, i.e. the LS mean treatment difference and its standard error, will be combined using Rubin's imputation rules (using the SAS MIANALYZE procedure) to produce a pooled LS mean estimate of treatment difference, its standard error and 95% CI, and a pooled p-value for the test of null hypothesis of no treatment effect.

Analyses will be conducted with different values of δ at each visit, which represents a percentage of the LS mean treatment difference at that visit, starting at 5% with 5% increments, until either the tipping point is identified or the 100% penalty is applied.

Document:

\

Author:

Version Number:
Version Date:Final 1.0
24FEB2020Template No: CS_TP_BS016 Revision 4
Effective Date: 01Apr2016

Reference: CS_WI_BS005

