5.4. MODIFIED INTENT-TO-TREAT [mITT] POPULATION

The modified intention-to-treat (mITT) population is defined as all subjects who were randomized, received at least one dose of study drug, and had a baseline and at least one post-baseline total score in SAPS-PD or NPI or CGI-S during the DB treatment period.

The mITT population will be the primary population for the efficacy analyses. Subjects will be analyzed according to randomized treatment group.

5.5. mITT COMPLETE CASES [mITTComp1] SAPS-PD POPULATION

The mITT complete cases (mITTComp) is defined as all subjects of the mITT who completed SAPS-PD assessment at the Week 6 visit (Visit 7 not including the ET visit), and have Baseline and Week 6 SAPS-PD total score data available. If a subject had missing SAPS-PD data at visits other than Week 6 (i.e. Visits 3 [Week 1], Visit 4 [Week 2], Visit 5 [Week 3], or Visit 6 [Week 5]), or if he had missing data in assessments other than SAPS-PD at Week 6 (Visit 7), this subject will still be included in the complete case analysis for SAPS-PD total score. Week 6 visit is defined in the protocol as study visit day 43 (+/-2 days). The mITT Complete cases population will be reviewed in a similar manner as the Per-Protocol population as some subjects may have performed a Week 6 visit outside of the visit window but they are still completers.

5.6. mITT COMPLETE CASES [mITTComp2] CGI-S POPULATION

Same as mITTComp1, for CGI-S instead.

The mITTComp1 and mITTComp2 populations will be used for the complete case analysis of the SAPS-PD total score and CGI-S score respectively. Subjects will be analyzed according to randomized treatment group.

Document:

\

Author:

Version Number:
Version Date:Final 1.0
24FEB2020Template No: CS_TP_BS016 Revision 4
Effective Date: 01Apr2016

Reference: CS_WI_BS005

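### The tipping-point search stops at 100% of the treatment difference, so it can end without the tipping value the SAP promises and leaves average outcomes beyond full loss of effect untested

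*SAP*

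**What the plan says.** SAP 15.1.4.3 describes the search twice. The opening description is open-ended: a series of analyses is run "with increasing values of δ until the analysis conclusion of a statistically significant treatment effect no longer holds". The δ that overturns the primary result is called the tipping point, and an interpretation of its clinical plausibility is promised. After MAR imputation, "a value of δ will be added to all imputed values in the SEP-363856 (25, 50 or 75 mg/day) group". Imputed scores must stay between 0 and 45.

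The closing paragraph sets the grid. δ differs by visit, "which represents a percentage of the LS mean treatment difference at that visit, starting at 5% with 5% increments", and the search continues "until either the tipping point is identified or the 100% penalty is applied". The section does not say what is reported if 100% is reached and the result is still significant.

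The neighbouring analysis, SAP 15.1.4.2, imputes SEP-363856 dropouts from the placebo model, "conditional on subject values observed at time points prior to discontinuation relative to the mean of the model for the placebo group". SAP 15.2.4 applies the same set of sensitivity analyses to CGI-S.

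**The concern.** A tipping-point analysis is meant to answer one question: how bad would the unobserved outcomes have to be before the conclusion changes? A cap at 100% of the estimated difference can stop the search before that question is answered. The promised tipping value and the judgement of its plausibility then do not exist, and a statement that no tipping point was found reflects where the grid ended. It could easily be read as broad robustness.

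The cap also sets the worst case. If δ is added after imputation, imputed SEP-363856 subjects lose at most the estimated drug effect on average. Lack of efficacy and adverse events are both listed reasons for discontinuation (Protocol 13.1, SAP 15.1.4.1), so average outcomes worse than that are a departure worth testing.

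**Working it through.** **Inputs.** About 24 SEP-363856 and 12 placebo subjects, two-sided 0.05 (SAP 3.4); δ grid from 5% to 100% of the visit difference (SAP 15.1.4.3). No dropout rate is stated, so the number of SEP-363856 subjects with an imputed Week 6 score, k, is an assumption.

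**The plan's own figure.** Noncentral t, 34 df, noncentrality ES/√(1/24 + 1/12), gives power of 59.4, 48.6, 37.8 and 28.0% at effect sizes 0.8, 0.7, 0.6 and 0.5. The SAP states 59, 48, 37 and 27%, so its figures are reproduced to within about one point.

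**Which results cannot tip.** Let D be the Week 6 difference. At the cap each of the k imputed scores worsens by D, so the difference becomes about D × (1 − k/24). With the SE fixed and a critical value of 2.04 (30 df, assumed), significance survives if |t| exceeds 2.04/(1 − k/24):

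- k = 2: 2.04/0.917 = 2.23
- k = 4: 2.04/0.833 = 2.45
- k = 6: 2.04/0.750 = 2.72

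**Penalty needed without a cap.** With imputed share d, the result tips at a penalty of (1 − t_crit/t_obs)/d, taking t_crit = 2.032 (34 df). For p = 0.01, t_obs = 2.728, so at d = 20% the penalty is (1 − 2.032/2.728)/0.20 = 128%.

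| Primary p | d = 10% | d = 20% | d = 30% |
|---|---|---|---|
| 0.04 | 48% | 24% | 16% |
| 0.02 | 168% | 84% | 56% |
| 0.01 | 255% | 128% | 85% |
| 0.001 | 436% | 218% | 145% |

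**How often the grid runs out.** Given a significant result, the fixed-SE chance of reaching 100% without tipping, at 10, 20 and 30% imputed, is 76, 52 and 30% for effect size 0.5, and 86, 68 and 47% for 0.8.

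A small multiple-imputation simulation (Week 6 ANCOVA, 25 imputations, AR(1) correlation 0.7, 60 significant trials per scenario) gave 67% at 15% dropout and 30% at 25% for effect size 0.8. If shifted values feed later visits, these become 50% and 18%. The Monte Carlo standard error is about √(0.67 × 0.33/60) = 6 points. The simulated values lie below the fixed-SE values at the neighbouring dropout rates, so holding the SE fixed probably overstates how often the search fails to tip.

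**Comparison with the placebo-based imputation.** In units of the Week 6 difference, the average placebo-based penalty is 1 − B·D(observed visits), where B holds the regression coefficients of Week 6 on the observed visits. Take an effect building as 0.25, 0.5, 0.8, 1.0 with AR(1) 0.7:

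- one observed visit: 1 − 0.343 × 0.25 = 0.91
- two: 1 − 0.49 × 0.5 = 0.76
- three: 1 − 0.7 × 0.8 = 0.44

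Across the effect profiles and correlations tried, the range was 0.06 to 1.00. The 100% δ penalty is 1.00 if added after imputation. If shifted values feed forward, it was 1.00 to 2.57. For the ramp after one observed visit, the shifts are 0.5, then 0.7 × 0.5 + 0.8 = 1.15, then 0.7 × 1.15 + 1.0 = 1.81.

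**The case against.** The closing paragraph of SAP 15.1.4.3 can be read as the operational rule for the principle stated earlier. It openly allows the search to end at 100%, and surviving a 100% penalty is informative: it shows robustness to full average loss of effect. That stands, but the reporting gap remains and the promised tipping value is still missing.

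A reader might infer that the capped series is never harsher than the placebo-based imputation, or merely repeats it. The documents do not support this. SAP 15.1.4.2 conditions on each subject's earlier scores, so benefit seen before dropout is partly carried forward. The 100% penalty is therefore on average as harsh or harsher. In the simulation it gave the less favourable estimate in 65–78% of significant trials, or 80–93% if shifts feed forward.

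A reader might also infer that subjects who leave with worsening psychosis are ignored. They are not. SAP 6.4 maps early-termination scores to the next planned visit, so recorded worsening counts as data and later imputations condition on it. This also means that k is not simply the number of dropouts: exit scores can fill Week 6, while off-period assessments are set to missing (SAP 6.9).

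Appendix 3 places the δ adjustment inside the sequential imputation step, so the effective penalty may exceed 100% and some results that the arithmetic says cannot tip could do so.

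Finally, the stakes are limited. This is one of six sensitivity approaches in SAP 15.1.4, in an exploratory trial with stated power of 27–59%, and it matters only if the primary result is significant.

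**Conclusion.** The point holds in a limited form. The two stopping rules in SAP 15.1.4.3 do not agree, and the cap can leave the analysis without its promised output. If δ is added after imputation, average outcomes worse than roughly complete loss of effect are not explored.

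The thresholds of about 2.2, 2.5 and 2.7 rest on the assumed 2, 4 or 6 imputed Week 6 scores among 24, 30 df and a fixed SE. It would go too far to say flatly that the search usually fails: that depends on a dropout rate which the documents do not give, and with about 25–30% imputed many significant results tip before the cap. The primary analysis is unaffected. This is a cheap improvement to a supportive analysis.

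**What to change.** In SAP 15.1.4.3:

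- Remove the 100% limit. Raise δ until significance is lost or all imputed SEP-363856 Week 6 scores are at the 45-point bound.
- Define δ as a positive, worsening shift in SAPS-PD points. A percentage of the LS mean difference is negative when the drug lowers SAPS-PD, so adding it literally would improve the imputed scores.
- State whether shifted values feed later visits, and make the text and Appendix 3 agree.
- Report the tipping δ in SAPS-PD points with its plausibility, or state explicitly that none was found.

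The CGI-S version under SAP 15.2.4 needs the same rule with its own scale maximum of 7. The cost is one or two sentences and a longer loop. The downside is that some δ values will be clinically implausible and must be described as such, a judgement the SAP already undertakes to make.
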